11.3.4 Relatedness of Adverse Event to Investigational Protocol

1. Not Related: Concomitant illness, accident, or event with no reasonable association with protocol.
2. Unlikely: The reaction has little or no temporal sequence from administration of the investigational protocol, and/or a more likely alternative etiology exists.
3. Possibly Related: The reaction follows a reasonably temporal sequence from administration of the investigational protocol and follows a known response pattern to the suspected investigational protocol; the reaction could have been produced by the investigational protocol or could have been produced by the subject's clinical state or by other modes of therapy administered to the subject.
4. Probably Related: The reaction follows a reasonably temporal sequence from administration of investigational protocol; is confirmed by discontinuation of the investigational protocol or by re-challenge; and cannot be reasonably explained by the known characteristics of the subject's clinical state.
5. Definitely Related: The reaction follows a reasonable temporal sequence from administration of investigational protocol; that follows a known or expected response pattern to the investigational protocol; and that is confirmed by improvement on stopping of the investigational protocol, and reappearance of the reaction on repeated exposure.

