5.4.2 Discontinuation of Treatment

Individual subjects will be allowed to continue in the study, but administration of the second immunization will be withheld if, after the first injection, any of the following criteria are met:

1. Any of the following serious adverse events attributable to BCG:
 - Life-threatening adverse event
 - Permanent or severe disability
 - Important BCG-specific medical events that do not result in death, are not life-threatening, and/or do not require hospitalization will be considered as serious if, based on appropriate medical judgment, they jeopardize the participant and would require medical or surgical intervention to prevent a serious adverse event.
2. Presentations of symptoms of disseminated BCG infection including persistent fevers, night sweats, weight loss. These symptoms usually do not occur within the timeline of the current study (usually 4 months to 2 years after vaccination), however should such symptoms occur prior to the second immunization, the treatment would be stopped.
3. The occurrence of any serious local skin reactions (\geq grade 3 ulceration, abscess formation, skin necrosis at the site of vaccination, or the development of suppurative lymphadenitis) as characterized by the standard FDA Toxicity grading scale (<https://www.fda.gov/regulatory-information/search-fda-guidance-documents/toxicity-grading-scale-healthy-adult-and-adolescent-volunteers-enrolled-preventive-vaccine-clinical>).

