6.2.2 Baseline Visit/BCG Vaccine 1 (Day 1)

All subjects who pass screening will return to MGH CNY for the Baseline visit. At this visit, all baseline clinical measures will be collected, and the first BCG vaccine injection will be administered. The Baseline visit will occur within 28 days of the Screening visit. If necessary, baseline measures may be collected up to 3 days before the Day 1 vaccination visit. The visit will take approximately three hours and will include:

- Vital signs
- Assess any changes to medical history, concomitant medications and/or adverse events
- Neurobehavioral assessments
 - RBANS
 - NPI-Q
- Phlebotomy for biomarker research
- Fasting lumbar puncture for biomarker research
- First BCG vaccine administration followed by 30 minutes of monitoring

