9.2 Lumbar puncture

Pain may occur during the procedure. This is usually temporary, confined to the lower back, and minimized with the cutaneous and soft tissue administration of 1% lidocaine as a local anesthetic. Short-lived LP associated headaches occur in <1%-36% of subjects with an incidence that decreases with age. Less commonly, a persistent low-pressure headache may develop as a result of a post-LP CSF leakage. Lower rates of post-LP headache have been noted with the atraumatic needles that will be prioritized for use in this study. Potentially more serious, but very rare risks, include infection, damage to radicular nerves and bleeding into the lumbar CSF space. The risk of these procedure related complications is much less than 1%. There is also a very rare risk of an allergic reaction to the lidocaine.

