Any adverse reaction that is serious, unexpected, and associated with the use of the product will be reported to the FDA in an IND safety report no more than 15 calendar days after the PI determines that the suspected adverse reaction qualifies for reporting, or 7 days for unexpected fatal or life-threatening adverse reaction reports.

The PI is responsible for classifying adverse events as serious or non-serious and determining if there is reasonable possibility that the drug was the cause. If the PI is not available to assess seriousness and relatedness

within 24 hours, a clinician investigator will make the assessment and speak with the PI as soon as they are available.

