11.3.3 Assessment of Adverse Events

At each visit (including telephone visits), the subject will be asked if they had any problems or symptoms since their last visit in order to determine the occurrence of adverse events. If the subject reports an adverse event, the Investigator will probe further to determine:

- Type of event
- Date of onset and resolution (duration)
- Severity (mild, moderate, severe)
- Seriousness (does the event meet the above definition for an SAE)
- Causality, relation to investigational protocol
- Outcome

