11.3.5 Recording of Adverse Events

All clinical adverse events are recorded in the Adverse Event (AE) Log in the subject's study binder. Study staff should fill out the AE Log and enter the AE information into the EDC system within 48 hours of learning of a new AE or receiving an update on an existing AE.

Entries on the AE Log (and into the EDC) will include the following: name and severity of the event, the date of onset, the date of resolution, relationship to investigational product, action taken, and primary outcome of event.

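### Adverse event causality is graded against the undefined investigational protocol, but the log needs relationship to the product, so lumbar puncture and BCG events may be misattributed in either direction

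*Combined protocol and SAP*

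**What the plan says.** Three parts of section 11.3 deal with causality, and they do not share one object.

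- 11.3.3 lists what the investigator establishes for each event, including "Causality, relation to investigational protocol".
- 11.3.4, headed "Relatedness of Adverse Event to Investigational Protocol", gives five levels from not related to definitely related. The lowest is "Not Related: Concomitant illness, accident, or event with no reasonable association with protocol", and the other four also refer to the investigational protocol. The term is not defined anywhere.
- 11.3.5 says what the log and the electronic data capture system must hold, including "relationship to investigational product, action taken, and primary outcome of event".

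Section 7 identifies the products as BCG and its diluent. The protocol also includes an LP of about 25 mL at Baseline and again at Day 84 (6.3.4), and research blood draws at Day 1, Day 28 and Day 84 (6.3.3). The Baseline visit in 6.2.2 lists the fasting LP and then "First BCG vaccine administration followed by 30 minutes of monitoring". It allows baseline measures up to 3 days before vaccination if necessary.

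Two other places ask a BCG-specific question without using the scale. Section 5.4.2 acts on "Any of the following serious adverse events attributable to BCG", and 11.3.1.1 makes the principal investigator responsible for "determining if there is reasonable possibility that the drug was the cause".

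**The concern.** Safety and tolerability of BCG is a stated secondary objective (3.2). The trial is open-label and everyone receives BCG (5.2), so there is no control arm to show the background rate of headache, back pain or malaise. The interpretation of adverse events therefore leans on case-by-case attribution.

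That attribution is asked in one form and stored in another. A rating against the protocol and a rating against the product can differ for the same event, and the plan does not say how one becomes the other. It has no field for relatedness to LP. The Baseline visit is the hard case, because timing cannot separate an LP from a vaccination given a few hours, or at most 3 days, later. Depending on how each investigator reads the scale, LP effects could enter the BCG profile, or systemic BCG symptoms could be dismissed as LP effects.

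**Working it through.** The plan gives no figure for relatedness, so there is none to reproduce. The check has two parts.

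**1. The same event under the two readings**

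*Headache the day after the Day 84 LP.* Dose 2 is given on Day 28 to Day 42 and the LP on Day 79 to Day 89. The gap is 79 − 42 = 37 days at the shortest and 89 − 28 = 61 days at the longest.
- Read against the protocol, the headache follows a protocol procedure and matches a pattern described in 9.2, so it is at least possibly related.
- Read against the product, the LP is a more likely alternative cause, so it is unlikely to be related.

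One scale gives two answers. Timing is not confounded here; the wording alone creates the difference.

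*Headache with malaise the day after Day 1.*
- Read against the protocol, it is at least possibly related, whichever procedure caused it.
- Read against the product, it could be unlikely (LP as the alternative cause) or possibly related (9.1 describes flu-like systemic effects lasting 1 to 2 days).

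Here timing does not help. The alternatives named under the possibly-related level are the participant's clinical state and other treatment, and a research LP is not clearly either.

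**2. How many events could be affected**

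Inputs:
- Headache rate: 9.2 says "Short-lived LP associated headaches occur in <1%-36% of subjects". This is per subject. I take <1% as 1% at the low end.
- Number of participants: 20 in 3.1, 12 in 7.4 and 8.1. That conflict is a separate matter, so both are run.
- Only the Day 1 LP is counted, because only that one coincides with a vaccination.

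Expected participants with headache = n × p; chance of at least one = 1 − (1 − p)^n.

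| n | p | Expected | At least one |
|---|---|---|---|
| 20 | 0.01 | 20 × 0.01 = 0.2 | 1 − 0.99^20 = 0.18 |
| 20 | 0.36 | 20 × 0.36 = 7.2 | 1 − 0.64^20 > 0.99 |
| 12 | 0.01 | 12 × 0.01 = 0.12 | 1 − 0.99^12 = 0.11 |
| 12 | 0.36 | 12 × 0.36 = 4.3 | 1 − 0.64^12 = 0.995 |

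At an assumed 10%, which is not a figure from the documents, the expected counts are 2.0 of 20 and 1.2 of 12.

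**The case against.** The strongest reply is that the plan already asks the right question where it matters. The log field is product relationship, 11.3.1.1 requires a drug-specific judgement, and 5.4.2 speaks of attribution to BCG. The numeric limb of the pause rule in 5.6 counts severe events whatever their cause. The scale's language about administration and re-challenge reads like a product scale with one noun changed, and its second level lets an investigator who reads it that way discount a typical post-LP headache. Section 6.3.4 also collects a survey on LP tolerability.

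Much of this stands, and it limits the point. No effect on a dosing, pausing or expedited-reporting decision is shown. But the judgement in 11.3.1.1 is ungraded and is not linked to the scale or to the log field. The survey records tolerability, not causality. That the scale can be read as a product scale shows the ambiguity; it does not remove it.

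Two stronger readings are tempting, and the documents do not support them.
- A reader might infer that LP events will be counted as BCG-related. Nothing says that the 11.3.4 grade is copied into the 11.3.5 field, and 8.1 defines no count or table of related events. The error could also run the other way.
- A reader might double the count for two LPs (0.36 × 40 = 14.4 events). That treats a per-subject rate as a rate per LP. It also includes the Day 84 LP, which comes 37 to 61 days after dose 2 and has no timing confound.

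Nor can it be said that LP headache would be the largest group of related events, because the documents give no rate for flu-like symptoms after BCG.

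**Conclusion.** The mismatch is real: causality is assessed and graded against an undefined protocol, and recorded against the product. No graded product scale, LP field or linking rule is given. The consequence is ambiguity, not inflation in a known direction. LP events may be recorded as BCG-related and BCG events may be put down to LP.

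For headache after the Day 1 LP, the exposure is 0 to about 7 of 20 participants, or 0 to about 4 of 12. The upper ends rest on the top of the range in 9.2 and should be read as bounds. The same section says that incidence decreases with age and that atraumatic needles, which have lower rates, are prioritised, and participants are aged 55 to 80. The calculation assumes that the per-subject rate applies to a single LP and that LP and dose 1 fall at the same visit, or within the 3-day allowance. The conclusion is the same at either sample size.

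In a single-arm pilot with BCG safety as an objective, this is worth correcting before adverse events are coded.

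**What to change.** - In 11.3.3 and 11.3.4, replace the investigational protocol with the investigational product as the object of the scale.
- On the adverse event form, record causality in three separate fields: (a) BCG, (b) lumbar puncture, (c) other study procedure.
- In 11.3.5, state that field (a) supplies the product relationship.
- In 8.1, state that field (a) defines a BCG-related adverse event, and add a table shell that shows the three fields separately.

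This point asks for no change to the wording of 5.4.2, which already refers to attribution to BCG. Tabulating events by period (dose 1 to dose 2, dose 2 to the Day 84 LP, after the Day 84 LP) is optional. It would help with the later periods, but the first would still mix LP and BCG.

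The cost is a case report form edit and a table shell. Onset dates are already collected under 11.3.5, and no visit, procedure or assessor is added.

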3 STUDY DESIGN

3.1 Overall Study Design and Plan

This single-site, open-label clinical trial will investigate the immune and neurobiological biomarker effects of BCG vaccination in healthy older adults and older adults with mild cognitive impairment (MCI), and gather data on tolerability, safety and study feasibility. Twenty participants (approx. n=10 cognitively normal, n=10 mild cognitive impairment) will receive two intradermal BCG vaccinations spaced 4 weeks apart and will be evaluated 12 weeks after the initial immunization. Cerebrospinal fluid (CSF) and blood will be collected at Screening (blood only), Baseline, Week 4 (blood only), and Week 12 for to assess safety, IIR and AD biomarkers.

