6.2.3 BCG Vaccine 2 (Day 28 + 14 days)

Subjects will be asked to return to MGH CNY for a second BCG vaccination visit 28 (+ 14) days after the first vaccination. This visit will take approximately one hour and will include:

- Vital signs
- Assess any changes to medical history, concomitant medications and/or adverse events
- Phlebotomy for safety labs
- Phlebotomy for biomarker research
- Vaccine site monitoring
- Second BCG vaccine administered followed by 30 minutes of monitoring

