6.2.5 Follow-up Phone Call (Day 98 ± 5 days)

All subjects who complete the Outcome visit will be called on Day 98 (± 5) days by the study coordinator or clinician to review changes to concomitant medications and/or adverse events.

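### The adverse-event relatedness scale does not fit a two-injection vaccine: a reaction first seen after dose 2 can never be rated Definitely Related (low severity, safety labelling only)

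*Combined protocol and SAP*

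**What the plan says.** Section 11.3.4 defines five relatedness categories.

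- *Definitely Related* (category 5) needs reasonable timing, a known or expected pattern, and that the reaction be "confirmed by improvement on stopping of the investigational protocol, and reappearance of the reaction on repeated exposure".
- *Probably Related* (category 4) needs reasonable timing, a reaction that "is confirmed by discontinuation of the investigational protocol or by re-challenge", and no reasonable explanation in the subject's clinical state.
- *Possibly Related* (category 3) needs reasonable timing and a reaction that "follows a known response pattern to the suspected investigational protocol". It must also be one that either the protocol, the clinical state or other therapy could have produced.
- *Unlikely* (category 2) needs "little or no temporal sequence from administration of the investigational protocol, and/or a more likely alternative etiology exists".
- *Not Related* (category 1) needs the absence of any reasonable association.

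On exposure, section 3.1 says participants "will receive two intradermal BCG vaccinations spaced 4 weeks apart". The Day 28 (+14) visit lists "Second BCG vaccine administered followed by 30 minutes of monitoring" (section 6.2.3). The Day 84 visit (section 6.2.4) lists no vaccination. The last contact is a telephone call: "All subjects who complete the Outcome visit will be called on Day 98", with a window of 5 days either side (section 6.2.5). Prior BCG exposure is excluded (section 4.1.1).

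On discontinuation, section 5.4.1 uses the word for leaving the study. Section 5.4.2 uses it for not giving dose 2: "administration of the second immunization will be withheld if, after the first injection, any of the following criteria are met". Section 11.3 refers to neither and gives no definition of its own.

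Causality is determined for each reported event (section 11.3.3) and entered in the AE log and EDC (section 11.3.5). Section 11.3.4 rates relation to the protocol, whereas section 11.3.5 records relation to the product.

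**The concern.** Dechallenge and re-challenge tests suit a drug taken continuously, which can be stopped and restarted. Here exposure consists of two single injections, and after the second there is nothing left to stop or repeat. A convincing BCG reaction after dose 2 may therefore be held at *Possibly Related* by the definitions, whatever the clinical evidence. Two careful raters who read discontinuation differently could also code the same event differently.

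Safety and tolerability is one of the two secondary objectives (section 3.2). The trial is open-label and all participants receive BCG (section 5.2), so no control-group event rate is available to separate BCG effects from background. The results are meant to inform later placebo-controlled trials (section 8.1). A causality field that is systematically capped for one of the two doses weakens that record.

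**Working it through.** No figure in the plan bears on this point, so the check sets the definitions beside the dosing schedule.

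**Step 1: which sequences can reach categories 4 and 5.** Assume reasonable timing and no reasonable explanation in the subject's clinical state.

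| Sequence | Later exposure? | *Definitely* | *Probably* |
|---|---|---|---|
| Dose 1 reaction, resolves, recurs after dose 2 | Yes (dose 2) | Open for a known or expected pattern, if resolution between injections counts as stopping | Open, through re-challenge |
| Dose 1 reaction, dose 2 withheld | None | Closed | Open, through discontinuation in the section 5.4.2 sense |
| First onset after dose 2 | None | Closed on any reading | Depends on the meaning of discontinuation |

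**Step 2: the meaning of discontinuation in the third row.**
- Leaving the study (section 5.4.1) can happen after dose 2 but removes no BCG exposure, so it confirms nothing.
- Withholding dose 2 (section 5.4.2) is impossible once dose 2 has been given.
- Resolution after the last injection would open *Probably*, but only for events seen to resolve, and the text does not state this reading.

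**Step 3: follow-up in which resolution could be seen.** Dose 2 falls on Day 28 to Day 42, and the last call on Day 93 to Day 103.
- Nominal: 98 − 28 = 70 days.
- Shortest: 93 − 42 = 51 days. Longest: 103 − 28 = 75 days.
- If the 28 (+14) days are counted from Day 1, dose 2 falls on Day 29 to Day 43. The range is then 93 − 43 = 50 to 103 − 29 = 74 days.

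Section 9.1 says that expected reactions, including lymphadenopathy, can last up to 3 months, about 91 days. A reaction of known pattern can therefore still be unresolved at last contact. It then stays at *Possibly* even on the third reading in step 2.

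**Step 4: what falls through the lower categories.** Take an unfamiliar, well-timed reaction with no likelier cause. It is not *Possibly* (no known pattern), not *Unlikely* (the timing is good and no other cause is likelier), and not *Not Related* (the timing is itself a reasonable association).
- First onset after dose 2: it fits no category unless resolution counts as discontinuation and the event has resolved.
- Onset after dose 1, dose 2 given, no recurrence: re-challenge is negative and nothing was discontinued. It too fits no category unless resolution between injections is counted.

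The gap therefore comes from the pattern requirement in category 3 and is not specific to dose 2.

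**Step 5: how many events.** The only usable frequency in the documents is for more severe skin or lymph-node reactions, 0.04% after a second vaccination (section 9.1). With 20 participants (section 3.1) that is 20 × 0.0004 = 0.008 expected events. With 12 (sections 7.4 and 8.1) it is 12 × 0.0004 = 0.0048. No frequency is given for milder events, so the number affected cannot be estimated.

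**The case against.** The strongest case against acting is that nothing operational depends on the five categories, and this stands. FDA reporting turns on whether BCG could reasonably have been the cause (section 11.3.1.1). The 24-hour rule covers every serious event (section 11.3.6). The pause rule counts any event of grade 3 or higher in three or more participants, whatever its relatedness (section 5.6). Withholding under section 5.4.2 is not mapped to the scale. All outcomes are exploratory and no analysis by relatedness is planned (section 8.1). Onset and resolution dates are recorded, so timing relative to dose 2 can be recovered. The expected vaccine-site reaction is not an adverse event at all (section 11.3.1).

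A reader might infer that BCG reactions would escape reporting or that stopping decisions would be distorted. For the reasons just given, the documents do not support that.

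A reader might also take the lymphadenopathy figure as evidence that unclassifiable reactions are likely. It is not: lymphadenopathy is a listed BCG reaction and so a known pattern, which category 3 can accommodate. Nothing in the documents shows how often an unfamiliar, unresolved reaction would arise. Nor does the sentence on shock or anaphylaxis in section 11.3.1.1 contradict the scale, because it concerns seriousness and not relatedness.

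The objection does not reach the definitions themselves. *Definitely* remains unreachable after dose 2, and *Probably* still turns on an undefined word.

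**Conclusion.** The point holds at low severity and is limited to safety labelling. For any reaction without a later injection, *Definitely Related* is closed by construction. For a first reaction after dose 2, *Probably Related* is open only on a reading that the protocol does not give. An unfamiliar, well-timed reaction with no likelier cause can be left without a category after either dose.

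This rests on three assumptions: no BCG is given after dose 2, as the schedule shows; raters apply section 11.3.4 as written; and the last limb of category 3 is met whenever the protocol could have produced the reaction. The number of affected events is unknown. For severe skin reactions after dose 2 it is close to zero.

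**What to change.** 1. In categories 4 and 5, apply the re-challenge test only where a further injection was given, and the dechallenge test only where a planned one was withheld. Where neither is possible, keep the other conditions of category 4 at full strength: reasonable timing, and no reasonable explanation in the subject's clinical state. Replacing the latter with a mere absence of a likelier cause would lower the bar after the last injection and make labels incomparable between doses. Where no re-exposure took place, category 5 should keep its known or expected pattern and also require specific confirmation already on record, so that timing alone does not suffice.
2. In category 3, let a known response pattern support the rating without being required. This closes the gap after both doses and makes the five categories exhaustive.
3. Add one sentence saying whether resolution after an injection counts as discontinuation or stopping. Reconcile it with sections 5.4.1 and 5.4.2, and reconcile protocol (section 11.3.4) with product (section 11.3.5).

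The cost is the wording of three definitions, one clarifying sentence and matching AE form guidance. No new tests or visits are needed, because confirmation counts only where a result already exists, for example from the additional testing that section 6.3.1.2 allows. The downside is that some events may be rated more strongly related. No change to dosing or withholding is proposed.
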